# **IV. SUBJECT ENROLLMENT**

This site will independently be studying the efficacy of ZX008 on seizure frequency in children and young adults with Sunflower Syndrome and the effects of ZX008 on EEG patterns and quality of life.

Informed consent will be obtained for each subject who participates in the study by the LPI and be documented in writing with the PHRC approved consent form. The LPI and/or the research nurse will initially explain the study, provide the informed consent form, and answer any questions from the subjects and their family members. Subjects will be given adequate time to make their decision. Subjects will have the opportunity to take the consent form home, and call back if they wish to participate. Subjects will also be encouraged to discuss any concerns they have with other health care providers. Informed consent for all subjects will be obtained by [name]., Ph.D.. The potential for coercion will be avoided through ensuring the subject that participation in the study is completely voluntary, and that deciding not to take part in the study will not affect the care or benefits to which the subject is otherwise entitled. Subjects will be enrolled in the study once informed consent has been obtained. Only the LPI will be obtain consent from the subject, the subject's parent/quardian or the subject's surrogate

For subjects who are older than 18 years of age with impaired decision making, and subjects under 18 years of age, legal consent to participate in research will be provided by a parent or an individual authorized under applicable state or local law to provide consent on the subject's behalf to general medical care. When enrolling a subject who is younger than 18 it is sufficient for consent to be obtained from just one parent. Before the LPI allows an individual other than a parent to consent on behalf of a child, she will document the basis for the individual's authority to consent on behalf of the child to general medical care and place any relevant documentation in the research file.

In addition to permission of the parent(s) or guardian, assent to participate in the study must be obtained from each child age 7 to 17 years old who, in the opinion of the LPI, is able to provide assent based on their age, maturity or psychological state. When obtained, assent for subjects 14 through 17 years of age will be documented using the PHRC approved Consent Form and assent for subjects 7 through 13 years of age will be documented in writing using the PHRC approved Assent Form. When assent is not obtained, the LPI will document the rationale in the research records.

The following categories of surrogates (listed in general order of preference) may provide consent in writing on behalf of potential subjects incapable of providing informed consent:

- 1. Court appointed guardian with specific authority to consent to participation in research or authority to make health care decisions for a class of diagnostic and therapeutic decisions inclusive of the proposed research;
- 2. Health care proxy/person with durable power of attorney with specific authority for making health care decisions inclusive of the proposed research; or
- 3. Spouse, adult child, or other close family member who knows the subject well and has been involved in their care.

Assent of subjects will be a requirement for participation in the research unless the subject is incapable of giving assent due to his/her medical condition. If the individual objects to participation, s/he will not be enrolled. When surrogate consent is relied upon, the LPI will ensure that the surrogate understands that his or her decisions should be based on "substituted judgment." This means that the decision reflects a potential subject's own views when s/he had the capacity to express them. The PHRC preferred order of surrogates will be followed,

and the Investigator will document the relationship of the surrogate to the subject in the research record.

# **V. STUDY PROCEDURES**

The investigational drug to be used in this study is fenfluramine hydrochloride (ZX008) manufactured by Zogenix, Inc..

ZX008 will be supplied as an oral solution in a concentration of 2.5 mg/mL. The subjects will be treated on an outpatient basis and will not require hospital admission. ZX008 will be administered on a twice daily basis.

The study will initially consist of a 4 week baseline period, during which handwaving associated with absence seizures and/or generalized tonic-clonic seizures will be recorded in a seizure diary on a daily basis. Subjects will meet enrollment criteria if they have an average of 6 generalized tonic-clonic and/or handwaving associated absence seizure per week.

If enrollment criteria is met, the subject will enter a titration period. The starting dose will be 0.2 mg/kg/day for the first 14 days. The dose will be increased every 2 weeks as tolerated by 0.2 mg/kg/day, to a maximum dose of 0.8 mg/kg/day, or a total maximum dose of 30 mg/day. The subject will remain on 0.8 mg/kg/day, 30 mg/day, or maximum tolerated dose for a 6 week maintenance period.

Site personnel will call the subject and/or their parent/caregiver every 11-14 days during the titration period before their next scheduled dose increase.

There will be 5 study visits within a 6 month period. After Visit 5, visits will occur every 6 months for an assessment in the clinic for subjects who respond to treatment with at least a 30% reduction in seizure frequency.

Seizure frequency will be tracked with the use of a daily seizure log. In the event that seizure frequency is markedly reduced compared to baseline after starting the study drug the LPI will discuss with the subject and/or their caregiver about adjusting the dose of concomitant seizure medications. If seizure frequency is markedly increased compared to baseline after discontinuing other medications which were taken as standard of care the LPI may decide to adjust dose of other seizure medications or reintroduce the medications that were taken as

IND Visit Schedule					
Visit Number	Visit Type	Time Point			
1	Baseline	Day -28			
2	Titration	Day 1 (+14 days)			
3	Titration and/or	28 days from Visit 2			
	Maintenance	(±7 days)			
4	Maintenance	56 days from Visit 2			
		(±14 days)			
5	Maintenance	84 days from Visit 2			
		(±14 days)			
Continuous	Maintenance	Each 6 Months			
		following Visit 5			
		(±14 days)			

part of standard of care. The use of these strategies will be decided on a case to case basis.

When applicable, at each study visit, subjects will be given an information sheet detailing the potential risk for adverse events seen up to that point, along with any other relevant study updates, how they will be monitored and what measures will be taken if a subject does experience an adverse event.

For each blood draw, approximately 5 mL of blood will be drawn from the subject.

#### At Visit 1, 2, 3, 4, 5, (Day -28, Day 1, Day 28, Day 56, Day 84) and All Sequential Visits

For the period during which COVID-19 contingency plans are in place at Partners/MGH, all study visits, including the Screening Visit, will be conducted as telemedicine appointments through a PHS IS-approved Zoom software. A weblink will be provided to subjects ahead of each appointment.

For study visits conducted as telemedicine appointments, required study procedures will be performed at sites local to the subject. We will provide each subject with location and scheduling information for their respective local site. The required study procedures that will be performed locally are:

- Echocardiograms (Visits 1, 5 and Extension Visits 1 and 2)
- Labs (CBC, CMP, AED) (as required by Principal Investigator)

Echocardiograms, and labs (CBC, CMP, AED) conducted locally will be sent to the Principal Investigator to ensure patient safety, and, in the case of ECHOs returning positive results, will be sent to a central reader, BioMedical Systems, Inc. (BMS).

These visits will take about 2 hours. During these visits, the following will be conducted:

- All the study eligibility criteria will be reviewed to confirm that the subject is still eligible.
- The subjects past and current medical, neurological, and epilepsy history will be reviewed at Visit 1 only.
- The study doctor will review the subject's current epilepsy status from the previous visit including: the amount of seizures they had, the types of seizures they experienced, and the duration of each of their seizure types.
- The subject will be asked about their health and the medicines that they have taken or are currently taking.
- Perform a physical and neurological exam. These exams are a series of simple questions and tests that provide very important information about the subject's systems. During the neurological exam, the treatment doctor will ask the subject to stand straight and walk, see how well the subject can move during the visit, and talk to the subject to see how they are doing. The treatment doctor will also look at the subject's eyes and see how their face, arms, and legs feel when touched.
- Vital signs including: blood pressure, heart rate, respiratory rate, along with height, and weight will be measured.
- If the subject is a female and able to become pregnant, a urine or blood pregnancy test will be done at every visit. The subject will not be allowed to enter or continue in the study if they are pregnant. If given permission, we will tell their parents the results of the test. If no permission is given, the study doctor may decide, based on the subject's age, maturity, or medical condition, to tell the subjects parents this information.
- Laboratory tests will be done. Approximately 5 mL (approximately 1 teaspoons) of blood will be taken from the subject's arm using a needle. The blood sample will be tested for: complete blood count with differential (CBC with diff) and a complete metabolic panel on Visits 1, 2, 3, 4, 5, and all subsequent visits. Current anticonvulsant medication levels will be tested on Visits 1, 3, 5, and on other Visits as clinically indicated. Laboratory tests will be completed locally and results sent to the Principal Investigator to ensure patient safety.

- The subject's seizure diary will be reviewed with the subject and/or their parent/caregiver. The subject and/or their parent/caregiver will record in their paper seizure diary daily. All of the subject's seizure types, along with the frequency and duration of each seizure, will be recorded in the subject's seizure diary. The subject and/or their parent/caregiver will record in the seizure diary if rescue medication was administered.
- Review of any current adverse events and/or adverse events of special interest experienced by the subject after the previous visit.
- The subject will be provided with new study drug bottles.
- During Visit 1, 5, and 7, a 4 to 6 hour electroencephalogram (EEG) will be performed (only for patients 1-10). This procedure will be done in order to analyze electrical activity in the brain. Changes in the brain wave patterns as well as photo paroxysmal response will be monitored.
- At Visit 1, 5 and all subsequent visits a Doppler echocardiogram (ECHO) will be done using ultrasound waves for examination of the heart. This will be performed at a cardiology clinic/office which may be separate from the study doctor's office, and may be done on a different day. The subject might receive a sedative medication for this procedure if they cannot be still for the test. In this test, the subject will be lying on a bed and a person will move a wand on their chest. This transmits information to a monitor to tell how well the subject's heart beats and moves inside their chest. It may also indicate if the subject has an increase in blood pressure in the arteries in their lungs. ECHOs will be completed locally and, if positive results are returned, it will be sent to a central reader, BioMedical Systems, Inc. (BMS) to ensure patient safety.
- At Visit 2, 5, and all subsequent visits, the subject and/or the subject's parent/caregiver will be asked to complete the following:
  - The Columbia-Suicide Severity Rating Scale (C-SSRS) questionnaire to see if they have ever thought about harming or killing themselves or behaved like they wanted to harm or kill themselves, if applicable.
  - Premonitory Urge Scale
  - If the subject is between 7-18 years he/she will be asked to complete:
    - the Beck Self Report Inventory to assess selfconcept, depression, anxiety, anger and disruptive behaviors
    - Children's Florida Obsessive-Compulsive Inventory

- Children's Yale-Brown Obsessive-Compulsive symptoms
- If the subject's age is 18 years or older he/she will be asked to complete:
  - Beck depression inventory.
  - Beck Anxiety inventory
  - Yale-Brown Obsessive-Compulsive symptoms
- The subject's caregiver/parent will be asked to complete questionnaires to measure the subject's health as it relates to quality of life, and how their condition affects their dayto-day activities and health. The questionnaires that will be given include:
  - Behavioral Rating Inventory of Executive Function (BRIEF) – to assess executive function
  - Quality of Life in Childhood Epilepsy Questionnaire (QOLCE) – to assess mood, social relationships, behaviors)
  - Attention Deficit Hyperactivity Disorder (ADHD) checklist – to assess for hyperactivity and inattention
- At Visit 2, Visit 5, and Visit 7, Neuropsychological testing will be done to assess cognitive function using the following tests (only for patients 1-10):
  - Weschler Abbreviated Scale of Intelligence (WASI-II subtests)
  - If the subject is between 7-16 years he/she will be asked to complete:
    - Weschler Intelligence Scale for Children (WISC-IV) -Working Memory subtests
    - Weschler Intelligence Scale for Children (WISC-IV) -Processing Speed subtests
  - If the subject's age is 16 years or older he/she will be asked to complete:
    - Weschler Adult Intelligence Scales IV (WAIS-IV)
    - WAIS IV Coding and symbol search
  - If a study visit is conducted via virtual visit, we will send subjects and their parent/caregiver the questionnaires via mail and the subjects will return them back to us after completion at the study visit.

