# The inclusion criteria for enrollment in this study include:

- Subject is male or non-pregnant, non-lactating female, age 4 to 25 years, inclusive as of the day of the screening visit. Female subjects of childbearing potential must have a negative serum pregnancy test at screening. Subjects of childbearing or child-fathering potential must be willing to use medically acceptable forms of birth control, which includes abstinence, while in this study and for 90 days after the last dose of study drug.
- Subjects must have a diagnosis of Sunflower Syndrome, where seizures are not completely controlled by their current treatment plan.

- Subjects must experience seizures including absence seizures and/or generalized tonic-clonic seizures which involve seeking out a light source, staring at the light source, and waving one hand in front of their eye(s). Subject's must experience an average of 6 handwaving associated with absence seizures and/or generalized tonic-clonic seizures per week.
- Evidence of EEG in the medical history that shows generalized spike and wave discharges between seizures and a strong photoparoxysmal response during photic stimulation. Acceptable evidence includes a copy of the EEG trace, EEG report, or physician note that appropriately describes the EEG findings.
- All medications or interventions for epilepsy must be stable for at least 4 weeks prior to screening and are expected to remain stable until Month 3.
- Subject and/or parent/guardian has been informed of the nature of the study and informed consent has been obtained from the subject and/or legally responsible parent/guardian.
- Subject has provided assent in accordance with Institutional Review Board (IRB)/Ethics Committee requirements, if capable.
- Subjects parent/caregiver is willing and able to be compliant with diary completion, visit schedule, and study drug accountability.

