#### Pregnancy/Birth Control

#### Women

If this subject is a female who is not able to have children, i.e. they are permanently sterile (when a female is unable to have children after surgical removal of female reproductive organ), they do not need to use any birth control methods.

Taking ZX008 may involve unknown risks to a pregnant female, an embryo, fetus (unborn baby), or nursing infant. Therefore, if the subject is pregnant, planning to become pregnant, or are breastfeeding a child, the subject cannot take part in this study.

Before entering the study, a blood pregnancy test will be done for all women who are able to become pregnant. This test might not detect an early pregnancy. Pregnancy tests will be repeated during the study.

Any female in the study who is sexually active and is able to have children must use, with her partner, approved methods of highly effective birth control from the time of signing informed consent through 90 days after the last dose of study drug. If the subject is already using a method of birth control, the study doctor or study staff will discuss with the subject whether their current method of birth control is acceptable for use during this study. Methods of effective birth control include surgical sterilization (for example, "vasectomy"); hormonal contraceptives such as birth control pills, the patch, intrauterine device, etc.

If during the study, the subject becomes pregnant, they should tell the study doctor as soon as possible. The study medication will be stopped, the subject will be discontinued from the study, and the study doctor will ask that the subject give updates about the outcome of the pregnancy.

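### The COVID-19 list of local procedures omits the pregnancy test and gives lab and ECHO timing that conflicts with the main visit schedule

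*Protocol*

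**What the plan says.** The contingency text is in Protocol Section V, under the heading that covers Visits 1 to 5 and all later visits. While the institution's COVID-19 plans apply, "all study visits, including the Screening Visit, will be conducted as telemedicine appointments". A general rule follows: "required study procedures will be performed at sites local to the subject". The text then turns specific, with "The required study procedures that will be performed locally are" and two bullets: "Echocardiograms (Visits 1, 5 and Extension Visits 1 and 2") and "Labs (CBC, CMP, AED) (as required by Principal Investigator").

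Other parts of the Protocol set these requirements, with no exception for telemedicine:

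- **Pregnancy test.** The inclusion criteria in Section III state: "Female subjects of childbearing potential must have a negative serum pregnancy test at screening". Section VII, under Women, says that before entry "a blood pregnancy test will be done for all women who are able to become pregnant". The Section V visit procedures add a urine or blood test at each visit for females able to become pregnant, and a positive result bars entry or continuation.
- **Labs.** The visit procedures fix CBC and CMP at Visits 1 to 5 and every later visit. AED levels are fixed at Visits 1, 3 and 5, and elsewhere when clinically indicated.
- **ECHO.** The visit procedures require it at Visits 1 and 5 and every later visit.

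**The concern.** The lead-in to the contingency list reads as complete, and the lab bullet spells out which assays it means. A coordinator booking local appointments from that list would order CBC, CMP and AED levels but no serum pregnancy test, could treat the blood work as optional, and would stop booking ECHOs after the second extension visit.

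These are safety rules. The pregnancy test decides entry and continuation in a study that enrols subjects aged 4 to 25 on a drug whose fetal risk the Protocol describes as unknown. The ECHO is the Protocol's stated safeguard against valve thickening and pulmonary hypertension, which it says develop slowly, so late ECHOs matter. Section VI lists the lab results among the variables collected from each subject, so discretionary labs would also leave gaps in the safety data. The telephone calls on Days 14, 42 and 70 do not fill these gaps: they cover adverse events and current medicines only.

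**Working it through.** No figure in the Protocol needs reproducing. The check sets the rules side by side, taking Visit 1 as the Screening Visit.

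| Item | Main rule | Contingency list | Difference |
|---|---|---|---|
| Serum pregnancy test | Screening (Section III; Section VII, Women) | Not named | Omitted |
| Urine or blood pregnancy test | Every visit (Section V) | Not named | Omitted |
| CBC and CMP | Visits 1–5 and all later visits (Section V) | At the investigator's requirement | Fixed against possibly discretionary |
| AED levels | Visits 1, 3, 5; others if indicated (Section V) | At the investigator's requirement | Fixed against possibly discretionary |
| ECHO | Visits 1, 5 and all later visits (Section V) | Visits 1, 5, Extension 1 and 2 | Differs from Extension 3 on |

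1. **Pregnancy test.** It is required at 5 of the 5 core visits and named on the local list for 0 of 5. A home urine kit could serve later visits, but it cannot meet a criterion that calls for serum.

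2. **Labs.** Two readings are possible. If the bullet gives the investigator discretion, the list guarantees CBC and CMP at 0 of 5 core visits against 5 of 5 in the visit procedures, and AED levels at 0 of 3 fixed visits against 3 of 3. If it only means as ordered under the protocol, the mismatch is zero. The text does not say which.

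3. **ECHO.** Extension visits are six months apart, so Extension Visit *n* falls nominally 6 × *n* months after Visit 5, taking Extension Visit 1 as the first six-monthly visit. Visits 1, 2 and 3 fall at 6, 12 and 18 months. The two texts agree through month 12 and part at month 18. Section V continues visits after Visit 5 for subjects with at least a 30% seizure reduction, so the gap concerns those still in follow-up then.

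4. **Is there a waiver or another route?** No section waives any of these items. Remote arrangements are written for other things: questionnaires are posted, and study drug is shipped home. The visit procedures say that laboratory tests and ECHOs are completed locally, so labs and ECHO have a route and only their timing conflicts. The statement on laboratory tests sits in the item that defines the blood sample as CBC, CMP and AED levels; the pregnancy test is a separate item.

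**The case against.** The strongest reply is that the requirements stay in force. The contingency text and the full procedure list share one heading, the full list follows directly, and the general rule sends required procedures to local sites. A serum pregnancy test could be run on the same screening draw as the CBC and CMP. All of that stands, and it keeps the point small. It does not remove the conflict, because the general rule is followed by a specific list that leaves the test out.

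Three stronger readings are tempting and are not supported:

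- **That a subject could be dosed without a pregnancy check.** Under the shipment section, drug is timed to arrive on the day of Visit 2 and must not be taken before that visit. Eligibility is reviewed and a pregnancy test is due at Visit 2. Shipment does not bypass the check, and nothing shows that any test was missed.
- **That weight and vital signs are dropped, putting mg/kg dosing at risk.** The visit procedures still state: "Vital signs including: blood pressure, heart rate, respiratory rate, along with height, and weight will be measured". Only the remote route is unstated, and a home weight is not excluded. The Protocol gives no basis for assuming any size of weighing error, so no dose consequence can be calculated. This is a clarification only.
- **That the list was meant to cut back monitoring.** A deliberate relaxation is possible for labs and late ECHOs, but the Protocol does not say so, and the visit procedures carry no exception.

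The list also leaves out the physical and neurological examinations and, for patients 1–10, the EEG and neuropsychological testing. So it may never have been meant as a full inventory, although its wording says otherwise.

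**Conclusion.** The conflict is real and of low severity. During the contingency, the local list names no pregnancy test, makes labs look discretionary and ends ECHO at Extension Visit 2. Each departs from a rule stated elsewhere in the Protocol and not waived.

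Its reach is limited: up to 20 subjects; the pregnancy item only for females able to become pregnant; the lab item only under the discretionary reading; and the ECHO item only from nominally 18 months after Visit 5 with the contingency still in force. No efficacy analysis is affected. The conclusion rests on reading the lead-in as a closed list, which is its plain wording, and on taking Visit 1 as screening and Extension Visit 1 as the first six-monthly visit.

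**What to change.** Amend the contingency list in Section V as follows:

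- Add a serum pregnancy test to the local screening draw, and a urine or blood test at each later visit, for females able to become pregnant.
- Replace the reference to the investigator's requirement with the schedule in the visit procedures: CBC and CMP at every visit; AED levels at Visits 1, 3 and 5 and when clinically indicated.
- Extend ECHO from Extension Visits 1 and 2 to every visit after Visit 5. If fewer ECHOs or labs are intended during the contingency, state that as an explicit exception.

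As a clarification in the same edit, say how weight and vital signs are obtained at a video visit, and whether the examinations, EEG and neuropsychological testing are done locally, deferred or omitted.

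The cost is a few words of amendment and possibly a few more local draws or ECHOs than the list's present wording would give. All of these are already required elsewhere in the Protocol.
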